9.3.2 Blinding

This is randomized, double-blind, placebo-controlled study. Subjects will be randomized in a 2:1 ratio to camostat mesilate:placebo. None of the investigators, study site personnel, Sponsor, or subjects will know to which treatment the subjects were randomized. To maintain the blind, camostat mesilate and placebo tablets will be indistinguishable from one another and are identified in distribution to study sites and dispensing to study subjects by a randomized number assigned to each bottle known only to the packager (Stason) and the IWRS.

The labeling, shipment, and receipt of the bottles at the study sites are all recorded in the IWRS software, contributing to the blinding of the assigned product after study randomization by preventing site personnel from knowing the exact contents of bottles assigned to study subjects. The assignment of the blinded randomization number to a subject and selection of a bottle number for the corresponding blind-labeled product bottle are controlled by the IWRS with no visibility of underlying study arm or product assignment to any party.

9.4 Dosage Modification

No dose modifications will be allowed.

9.5 Treatment Accountability and Compliance

The pharmacist or other designated individual will maintain electronic records of study drug delivered to the study site, the inventory at the study site, the distribution to and use by each subject, and the return of materials to the Sponsor for storage or disposal. These records should include dates, quantities, batch/serial numbers, expiration dates, in-clinic temperature logs, and unique code numbers assigned to the product and study subjects.

At each visit after initiation of treatment, study site personnel will record compliance. Subjects will be instructed to bring their unused/partially used bottles back for inspection at each study visit. Subjects are to be reminded of the importance of compliance with an emphasis on taking their study drug on schedule and maintaining the prescribed interval between doses.

Investigators will maintain records that adequately document that the subjects were provided with the correct study treatment allocation and reconcile the products received from the drug

dispensing center. Used or unused Investigational product will be returned to Stason Pharmaceuticals, Inc. (drug packager) if not destroyed at the clinical site.

Medication containers must be returned at the end of treatment visit, as compliance will be assessed by tablet counts. Noncompliance is defined as taking less than 80% of study drug. Discontinuation for noncompliance is at the investigator's discretion and is to be noted on the eCRF.

9.6 Prior and Concomitant Therapies/Interventions

9.6.1 Prior and Concomitant Medications

Restricted prior therapies are provided in [Section 8.2](#) and are prohibited within 30 days before the time of screening. All medications taken by or administered to the subject within 30 days of screening will be recorded on the eCRF.

After the baseline visit, medication to treat minor treatment-emergent illness is generally permitted; however, the following therapies are expressly prohibited throughout the study:

- Any antiviral medications, including but not limited to, hydroxychloroquine, lopinavir/ritonavir, tocilizumab, ivermectin, or remdesivir
- Experimental drug or off-label use of any drug.
- Antipyretics are not allowed with the exception of acetaminophen.

Any medication or therapy that is taken by or administered to the subject during the course of the study must be recorded on the eCRF. The entry must include the dose, regimen, route, indication, and dates of use.

Cough expectorants (e.g., guaifenesin) and cough suppressants (e.g., dextromethorphan) are allowed during the study.

Acetaminophen for fever is allowed

Antihistamines are allowed for congestion

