COVID-19 is diagnosed by using reverse transcriptase-polymerase chain reaction (RT-PCR) from a nasopharyngeal swab sample. The sensitivity of this assay is high but not 100%; therefore repeat testing is important if the person continues to exhibit symptoms, has knowingly been exposed, or lives in an area where there are a high number of COVID-19 cases ([Gandhi et al, 2020](#)).

The most common symptoms of a mild to moderate COVID-19 infection are fever, cough, sore throat, malaise, and myalgia. Anorexia, nausea, diarrhea, anosmia, and ageusia are often reported. Dyspnea may occur (usually 5 to 8 days after symptom onset) and is suggestive of more severe disease, often a precursor to hospitalization. Dyspnea can occur in patients with moderate disease but the oxygen saturation is usually at least 94% on room air ([Gandhi et al, 2020](#)). Importantly, clinical deterioration typically does not occur until more than 5 to 7 days following symptom onset, suggesting there is a window of opportunity for antiviral therapy early in the infection prior to the subsequent onset of severe systemic inflammation.

Certain comorbid conditions render a person more susceptible to contracting COVID-19 and contribute to worsening of the disease to a more severe version. These conditions include: age ≥ 65 years, cardiovascular disease, chronic lung disease, hypertension, diabetes, obesity, and diseases that weaken the immune system ([Gandhi et al, 2020](#)).

Patients with mild or moderate COVID-19 are usually instructed to recover at home, where they can be isolated, observed, monitored, and receive supportive care. However, some patient's conditions may deteriorate, especially those with comorbid conditions, which most often happens a week after onset of symptoms. These patients should be monitored closely. Patients with mild to moderate disease are able to monitor their own oxygen saturation levels if they are given a pulse oximeter ([Gandhi et al, 2020](#)).

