Other than supportive care, remdesivir is the only treatment at this time that has proven efficacy from a Phase 3 randomized, placebo-controlled clinical trial, but, importantly, this was only administered to hospitalized patients with severe COVID-19. A preliminary report of early unblinding of the results showed a statistically significant, shortened time to recovery in the group that received remdesivir (11 days) compared with those who received placebo (15 days). Kaplan-Meier estimates of mortality by 14 days were 7.1% for remdesivir and 11.9% for placebo, which was not a statistically significant difference ([Beigel JH et al, 2020](#)). There currently is no vaccine that provides immunity against COVID-19.

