7.1 Description of Overall Study Design and Plan

This is a randomized, double-blind, placebo-controlled study of camostat mesilate in ambulatory outpatients with confirmed COVID-19 with at least one risk factor for severe illness. Subjects will be randomized in a 2:1 ratio of camostat mesilate:placebo. Approximately 300 subjects are planned to be enrolled (200 subjects to camostat mesilate and 100 subjects to placebo). Subjects will be treated with camostat mesilate 200 mg orally QID for 14 days and receive local SOC in addition to study drug. Subjects in the control arm will receive 2 placebo tablets orally QID for 14 days, as well as local SOC. All subjects will be followed until Day 28. Subjects will complete a symptom eDiary daily from Day 1 (first dose of study drug) through Day 15. Subjects will be coming into the clinic for assessments on Day 1, Day 7 and Day 15. Mid-turbinate nasal samples will be obtained at Screening, Day 7 and Day 15. Instructions for obtaining proper nasal samples will be provided. Subjects who withdraw from the study prior to completion of the 14-day

treatment period will be asked to return for an Early Termination visit for blood draws and a mid-turbinate swab collection. On Day 28 (end of study), a study team member will record subject disposition.

Figure 1 presents the study design.

Figure 1. Study Schematic

Abbreviations: COVID-19 = coronavirus disease 2019; SOC=standard of care.

^a The Screening/Baseline and Day 1 visit assessments can be done on the same day.

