8.1 Inclusion Criteria

Individuals must meet all of the following criteria to be included in the study:

1. Adults willing and able to provide informed consent before performing study procedures
2. Adults aged ≥ 18 years at time of informed consent
3. Subjects must have written notification of laboratory confirmed COVID-19 infection performed prior to screening, at a local laboratory by RT-PCR or other commercial or public health assay in any specimen. Subjects should be randomized within 72 hours of receiving this notification.

(NOTE: all subjects will also undergo RT-PCR testing of mid-turbinate samples at a central laboratory on a specimen collected during the Screening/Baseline and Day 1 visit, but entry to the study is based on previously completed local testing for clinical purposes).

4. Have a mild or moderate form of COVID-19 defined as a SpO₂ > 94% at screening
5. Subjects must have at least 1 of the following risk factors for severe illness:
 - a. Aged 65 years or older
 - b. Hypertension
 - c. Diabetes mellitus
 - d. Chronic lung disease including asthma, chronic obstructive pulmonary disease (COPD), and interstitial lung disease (e.g., idiopathic pulmonary fibrosis)
 - e. Chronic cardiac conditions, including coronary artery disease (CAD), heart failure, congenital heart disease, cardiomyopathy
 - f. Severe obesity (body mass index [BMI] ≥ 40 kg/m²)
 - g. Chronic liver disease, including cirrhosis
6. Must agree not to enroll in another study of an investigational agent or take any other drug that has been granted Emergency Use Authorization prior to completion of Day 28
7. If women of childbearing potential (WOCBP) or men whose sexual partners are WOCBP, must be able and willing to use at least 1 highly effective method of contraception during the study and for 90 days after receiving the last dose of study drug. A female subject is considered to be a WOCBP following menarche and until she is in a postmenopausal state for 12 months or otherwise permanently sterile (for which acceptable methods include hysterectomy, bilateral salpingectomy, and bilateral oophorectomy). Contraceptive use by men or women should be consistent with local regulations regarding the methods of

contraception for those participating in clinical studies. Information on contraceptive use during the study is presented in [Appendix 1](#).

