8.2 Exclusion Criteria

Individuals meeting any of the following criteria at screening or baseline are ineligible to participate in this study:

1. Physician makes a decision that trial involvement is not in subjects' best interest, or any condition that does not allow the protocol to be followed safely
2. Known severe liver disease (e.g., Child Pugh score > 12, AST > 5 times upper limit)
3. Oxygen saturation (SaO₂)/SpO₂ ≤ 94% in room air condition, or the arterial oxygen partial pressure (PaO₂)/fractional inspired oxygen (FiO₂) ratio < 300 mmHg
4. Known allergic reaction to camostat mesilate or one of its excipients
5. Known severe renal impairment or receiving dialysis
6. Pregnant or breastfeeding, or positive pregnancy test in a pre-dose examination
7. Receipt of any experimental treatment for COVID-19, including agents with actual or possible direct acting antiviral activity, including, but not limited to, hydroxychloroquine, lopinavir/ritonavir, tocilizumab, ivermectin, or remdesivir within the 30 days prior to the time of the screening evaluation. No off-label use of a drug for COVID-19 is allowed.
8. History of human immunodeficiency virus infection on highly active antiretroviral therapy (HAART).

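### Section 9.6.1 bars remdesivir, other antivirals and off-label drugs for the whole study, with no exception once a subject is admitted with COVID-19

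*Protocol*

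**What the plan says.** Protocol 9.6.1 allows medication for minor illness after baseline, then states that "the following therapies are expressly prohibited throughout the study". The list covers any antiviral (remdesivir and tocilizumab are among those named), experimental drugs, and off-label use of any drug. The section gives no end date. Section 7.3 places the end of study at the Day 28 visit, and 7.1 says "All subjects will be followed until Day 28". Inclusion criterion 6 has a parallel undertaking: subjects must agree not to "take any other drug that has been granted Emergency Use Authorization prior to completion of Day 28".

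On treatment, 5.1.1 says that, supportive care apart, "remdesivir is the only treatment at this time that has proven efficacy from a Phase 3 randomized, placebo-controlled clinical trial", and adds that "this was only administered to hospitalized patients with severe COVID-19". Section 7.1 provides that subjects "receive local SOC in addition to study drug".

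Section 11.2 makes COVID-19 related hospitalization part of the primary event and counts an emergency room presentation as hospitalization. Section 8.5 asks sites to follow discontinued subjects to Day 28 for all outcomes, but lists hospitalization, beside death, withdrawal of consent and loss to follow-up, as an exception.

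**The concern.** A ban on other antivirals makes sense while the subject is an outpatient at risk of the primary event, because such drugs could change whether the event happens. Once a subject is admitted for COVID-19 the event has happened, and the ban no longer protects the primary endpoint. It then covers the one drug that the protocol itself describes as proven in severe inpatients.

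Two things are at stake. Sites have no written rule that lets an admitted subject receive standard inpatient treatment within the protocol. And if the site resolves the conflict by withdrawing the subject, 8.5 no longer asks for Day 28 follow-up, in the group where Day 28 survival, a secondary endpoint, is most informative.

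**Working it through.** **Size.** Inputs: 15% and 30% event rates (Protocol 13.1, SAP 4.1.4); 186 and 93 subjects (SAP 4.1.3); 200 and 100 subjects planned (Protocol 7.1).

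- The SAP's own count: 186 × 0.15 = 27.9 on camostat and 93 × 0.30 = 27.9 on placebo. This reproduces its figure of nearly 28 per arm, 55.8 of 279 in total.
- At the planned enrolment: 200 × 0.15 + 100 × 0.30 = 30 + 30 = 60 of 300.

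Sixty is a ceiling. Emergency room visits without admission and deaths without admission also count as events, and 5.1.1 ties remdesivir's proven efficacy to severe disease. The documents give neither the share admitted nor the share severe, so the number affected lies somewhere between 0 and about 60.

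**How long the ban lasts.** Day 28 is not written in 9.6.1. It follows from the whole-study wording read with 7.1 and 7.3. Criterion 6, which names Day 28, points the same way.

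**Whether anything lifts it.** Four texts come near an exception:

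- 7.1, local standard of care: a general provision that does not say it overrides a drug-specific prohibition.
- 8.5, withdrawal: participation may end on the investigator's clinical judgment, or when a changed condition makes the subject ineligible for further treatment. Both are permissive. Neither makes admission a withdrawal event or permits the listed drugs.
- 10.3, efficacy assessments: death is recorded for subjects not hospitalized. This suggests that admission closes the efficacy record, but it sets no rule on treatment.
- SAP 3.1: hospitalization, ER visit and death are recorded on the End of Study form. This says where the data come from, not that participation ends on admission.

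None is an exception.

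**What follows for an admitted subject given remdesivir.** Either the subject stays in the study and the treatment is a protocol deviation, or the subject is withdrawn; 8.5 also lists failure to adhere to the protocol among the reasons for withdrawal. After withdrawal the hospitalization exception in 8.5 applies, and vital status at Day 28 may not be collected. SAP 4.2.1 analyses survival by the primary endpoint's approach, and the imputation variables listed in SAP 4.1.7 do not include hospitalization.

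**What does not change.** The primary endpoint is binary and already met at COVID-19 admission. Time to hospitalization or death is also fixed by then. Treatment given afterwards alters neither, nor the sample size.

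**The case against.** The strongest reply is that 9.6.1 is guidance for outpatients. Its sentence opens with minor illness, and the section goes on to cough remedies, acetaminophen and antihistamines. Section 7.1 provides local standard of care, 8.5 lets the investigator end participation at any time, and the trial runs under GCP and the Declaration of Helsinki. The hospitalization wording in 8.5 and 10.3 and the End of Study form can be read as treating admission as the end of active participation. On that reading nobody goes untreated.

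Much of this stands. A reader might infer that the protocol would deny remdesivir to admitted subjects. The documents do not support that as the likely outcome; a logged deviation or a withdrawal is more plausible. But none of these texts authorises the listed drugs or says that participation ends on admission, and 7.1 follows everyone to Day 28. A site that follows the text still meets an express prohibition.

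A second reply is that the ban still serves secondary endpoints, since survival and viral shedding would otherwise reflect inpatient treatment. That is a real trade-off but a weak reason to keep the rule. It affects only secondary outcomes in admitted subjects, and the alternative risks having no Day 28 survival status for them.

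**Conclusion.** The gap is real and modest. It rests on reading the whole-study wording as running to Day 28, which 7.1 and 7.3 support but 9.6.1 does not state; confidence is therefore moderate. At planned rates at most about 60 of 300 subjects have a primary event, and fewer would be admitted with severe disease.

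Three further inferences should be resisted:

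- That the primary result is biased. The ITT analysis is primary, and its endpoint is already met at COVID-19 admission.
- That criterion 6 bars remdesivir a second time. The documents do not say that remdesivir has an Emergency Use Authorization, so that clause matters only for consistency.
- That Day 28 survival will be missing for all admitted subjects. The exception in 8.5 applies only after discontinuation, and it excuses follow-up without forbidding it.

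This is mainly a patient-care and site-guidance point, with a possible loss of secondary data. It is a cheap improvement.

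**What to change.** 1. Amend 9.6.1 so that the prohibition ends at COVID-19 inpatient admission, after which local standard of care, including remdesivir, is allowed. Use the term inpatient admission: 11.2 counts an emergency room visit as hospitalization, and a visit without admission should not lift the ban. The eCRF entry that 9.6.1 already requires, with dose and dates, is enough to record it.
2. For consistency, add the same exception to the Emergency Use Authorization clause of inclusion criterion 6 and to the matching synopsis text. The bar on joining another investigational study stays.
3. State whether study drug stops at admission. Otherwise an admission during the 14 treatment days leaves open whether blinded study drug continues alongside remdesivir.
4. Delete hospitalization from the follow-up exceptions in 8.5, so that vital status is still collected to Day 28.

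The cost is a few sentences in the protocol, with no change to the ITT primary analysis or the sample size. The downside is that Day 28 survival, and Day 15 shedding in admitted subjects, will reflect in-hospital care. At planned rates up to 30% of placebo and 15% of camostat subjects have a primary event, so that care could be used more on placebo. The survival comparison should be described accordingly.

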10 STUDY PROCEDURES

[Table 1](#) outlines the timing of procedures and assessments to be performed throughout the study. [Section 12.3](#) specifies laboratory assessment samples to be obtained. See [Section 11](#) and [Section 12](#) for additional details regarding efficacy assessments and safety assessments, respectively.

Table 1. Schedule of Assessments

Study Day:	Screening/Baseline & D1 ^{a,b}	D2	D3	D4	D5	D6	D7	D8	D9	D 10	D 11	D 12	D 13	D 14	D 15	D 21	Unscheduled Visit ⁱ	End of Study D 28	Early Termination
Assessment / Procedure																			
Informed consent ^a	X																		
Verify notification of local COVID-19 positive test result occurred within 72 hours of screening ^a	X																		
Eligibility criteria ^a	X																		
Demographics ^a	X																		
Medical history ^a	X																		
Concomitant medications ^a	X						X								X	X	X		
Urine pregnancy test (as applicable) ^a	X																		
Clinic visit ^d	X						X ± 1 day								X ± 1 day	 ± 1 day	X	 ± 1 day	X ± 1 day
Height / Weight ^d	X																		
Randomization, assign subject ID, dispense study drug ^b	X																		
Complete eDiary ^{c,e}	X	X	X	X	X	X	X	X	X	X	X	X	X	X	X				
Vital signs (heart rate, blood pressure, SpO2) ^a	X						X								X		X		X
Adverse events ^{a,g}	X						X								X	X	X		X
Laboratory assessments ^{a,g}	X														X		X		X

This document is confidential.

Study Day: Assessment / Procedure	Screening/Baseline & D1 ^{a,b}	D2	D3	D4	D5	D6	D7	D8	D9	D 10	D 11	D 12	D 13	D 14	D 15	D 21	Unscheduled Visit ⁱ	End of Study D 28	Early Termination
Sample for viral shedding by RT- PCR (mid-turbinate swab) ^a	X						X								X				X
Body temperature assessment ^{a,c,h}	X	X	X	X	X	X	X	X	X	X	X	X	X	X	X	X	X	X	X
Study drug administration	X	X	X	X	X	X	X	X	X	X	X	X	X	X					

Abbreviations: AE = adverse event; ALT = alanine transaminase; ALP = alkaline phosphatase; AST = aspartate aminotransferase; BUN = blood urea nitrogen; CBC = complete blood count; COVID-19 = coronavirus disease 2019; CRP = C-reactive protein; D = day; GGT = gamma-glutamyl transferase; ID = identification; LDH = lactate dehydrogenase; MCV = mean corpuscular volume; RBC = red blood cell; RT-PCR = reverse transcriptase – polymerase chain reaction; SAE = serious adverse event; SpO2 = peripheral capillary oxygen saturation; WBC = white blood cell.

- ^a Denotes a baseline assessment. Baseline is defined as before the first dose of study drug. Baseline assessments should be performed before administration of study drug. Subjects are enrolled following completion of eligibility requirements and who are randomized in the IWR. Subjects who are screened to determine eligibility, but do not undergo any baseline assessments are not considered enrolled. All eligible subjects must have documented COVID-19 infection diagnosed at the local level.
- ^b Study Day 1= first dose of study drug.
- ^c Assessments to be done daily.
- ^d X = clinic visit, ☎ = telephone visit. All post-baseline visits are ± 1 day in the event a visit occurs on a weekend.
- ^e Subjects will be given access and instructions to complete their eDiary on Day 1 using the web portal. Subjects will complete their eDiary daily from Day 1 through Day 15, Data to be collected in the eDiary daily will include 1) the number of study medication doses taken/missed and 2) the highest temperature recorded over the past 24 hour period.
- ^f All AEs must be recorded from the time of administration of the first dose of study drug until the subject has completed the end of study or early withdrawal. Any study procedure-related SAE that occurs after the study participant has signed the informed consent form and prior to administration of the first dose of study drug will be considered as Medical History. The study will collect only Treatment Emergent Adverse Events (TEAE).
- ^g Laboratory assessments including hematology (CBC including hemoglobin, hematocrit, WBC with differential, RBC, MCV, and platelet count) and clinical chemistry (albumin, ALT, ALP, AST, BUN, GGT, creatinine, electrolytes [sodium, potassium, carbon dioxide, chloride], glucose, total bilirubin, direct bilirubin, LDH, CRP) will be collected. Laboratory tests will be performed at the central laboratory.
- ^h Absence of fever is defined as ≤ 37.2°C oral.
- ⁱ The indicated assessments may be done at the investigators discretion but are not required.

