6.2.2 Secondary Endpoints

Survival/Mortality

- The overall survival rate (the proportion of randomized subjects who survive up to Day 15 and Day 28)

Clinical Improvement

- Time to resolution of fever from randomization up to Day 28
- Time to hospitalization or death following randomization up to Day 28
- Proportion of subjects with no viral shedding (yes/no) using RT-PCR at Day 7, Day 15, and at Early Termination (for subjects withdrawn prior to completing the 14-day treatment period)

Safety/Tolerability

- Incidence of AEs and SAEs of any grade from randomization up to Day 28
- Cumulative incidence of grade 3 and 4 AEs from randomization up to Day 28
- Incidence of discontinuation from study due to an AE/SAE (discontinued subjects will be followed up until Day 28)
- Change from baseline in clinical laboratory parameters
- Change from baseline in vital signs (heart rate, blood pressure, peripheral capillary oxygen saturation [SpO₂])

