10.1 Study Visits

10.1.1 Screening/Baseline and Day 1 Visit

The following procedures and assessments will be done at the onsite Screening/Baseline and Day 1 visit:

- Verify subject has written notification from a local laboratory confirming COVID-19 infection within 72 hours of randomization (i.e., Day 1). In most instances, the Screening/Baseline visit will occur on the same date as Day 1. If needed, the Screening/Baseline may occur before Day 1 as long as randomization can be completed within the 72-hour window.
- Obtain informed consent
- Review of inclusion/exclusion criteria, including urine pregnancy test, if applicable
- Assign a subject ID number (ID number = XXX site number followed by 001, 002, 003 subject number)
- Obtain mid-turbinate nasal swab sample to be sent to the central laboratory to test for a baseline assessment and to test for viral shedding of COVID-19 by RT-PCR
- Draw blood for central laboratory testing
- Record demographics, medical history (including current COVID-19 symptoms), and concomitant medications
- Obtain vital signs (height, weight, heart rate, blood pressure, SpO2)
- Measure oral body temperature
- Perform randomization and dispensing of study drug
- Provide subject with instructions for accessing eDiary portal for collection of daily information
- Administer first dose of study drug after all assessments are completed
- Record of any TEAEs

10.1.2 Onsite Visits on Day 7, Day 15, Unscheduled Visit, Early Termination Visits / Telephone Visits on Day 21, Day 28

The following procedures and assessments will be done on Day 7, Day 15, Day 21, Day 28, and early termination by telephone or at onsite visits:

- Verify subject compliance for completing daily eDiary entries by accessing the web portal for the subject's eDiary
- Review concomitant medications and record any TEAEs
- Assess vital signs (heart rate, blood pressure, SpO2) during on-site visits only
- Measure oral body temperature
- Draw blood for central laboratory testing (Day 15, Unscheduled Visit and Early Termination) during on-site visits only

- Obtain mid-turbinate nasal swab sample for viral shedding test (Day 7, Day 15, and Early Termination Visits) for central laboratory during on-site visits only

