12.4 Adverse Events

12.4.1 Adverse Events

An AE is any symptom, physical sign, syndrome, or disease that either emerges during the study or, if present at screening, worsens during the study, regardless of the suspected cause of the event. All medical and psychiatric conditions (except those related to the indication under study) present at screening will be documented in the medical history eCRF. Changes in these conditions and new symptoms, physical signs, syndromes, or diseases should be noted on the AE eCRF during the rest of the study.

Subjects will be instructed to report AEs at each study visit. All AEs are to be followed up until resolution or a stable clinical endpoint is reached.

Each AE is to be documented on the eCRF with reference to date of onset, duration, frequency, severity, relationship to study drug, action taken with study drug, treatment of event, and outcome. Furthermore, each AE is to be classified as being serious or nonserious. Changes in AEs and resolution dates are to be documented on the eCRF.

For the purposes of this study, the period of observation for collection of AEs extends from the time the subject is administered study medication (Day 1) until Day 28 or early termination. Subjects with early termination will be followed up until Day 28. Follow-up of the AE, even after the date of therapy discontinuation, is required if the AE persists until the event resolves or stabilizes at a level acceptable to the investigator.

When changes in the intensity of an AE occur more frequently than once a day, the maximum intensity for the event should be noted. If the intensity category changes over a number of days, then those changes should be recorded separately (with distinct onset dates).

Specific guidelines for classifying AEs by intensity and relationship to study drug are given in [Table 3](#) and [Table 4](#).

Table 3. Classification of Adverse Events by Intensity

MILD: An event that is easily tolerated by the subject, causing minimal discomfort and not interfering with everyday activities.

MODERATE: An event that is sufficiently discomforting to interfere with normal everyday activities.

SEVERE: An event that prevents normal everyday activities.

Table 4. Classification of Adverse Events by Relationship to Study Drug

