4.3.1 Summary of Adverse Events

All analyses of adverse events will be based on the Safety Population. A summary of the numbers and percentages of patients within each treatment group experiencing at least one treatment emergent-adverse event (TEAE) will be provided in tables. A treatment emergent-adverse event is any AE that occurs after any exposure to treatment.

A Relative Risk comparison of the incidence in Camostat mesilate to Placebo will also be provided including a 95% Binomial Exact Confidence Interval when at least 3 subjects in both groups experienced the event.

TEAEs will be defined as an AE occurring from Day 1 to end of study which is defined as Day 28. 'Drug-related' is defined as 'possibly,' 'probably,' or 'definitely' caused by the study medication.

The AE endpoints summarized in this table are:

- With one or more TEAE
- With one or more drug-related TEAE
- With one or more serious TEAEs
- With one or more serious drug-related TEAE
- With one or more severe TEAE
- With one or more moderate or severe TEAE
- TEAE with outcome of death
- TEAE with outcome of drug related death
- Discontinued study drug due to AE/SAE
- Discontinued from study due to AE/SAE

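### Table 1, its footnote f and one sentence of Section 12.4.1 end adverse-event collection at early withdrawal, and Table 1 shows no Day 28 mark, in conflict with the Day 28 safety window elsewhere in the protocol and SAP

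*Protocol*

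**What the plan says.** **Text that stops at withdrawal**
- Protocol Table 1, footnote f: AEs are recorded from the first dose "until the subject has completed the end of study or early withdrawal".
- Protocol 12.4.1 sets the collection period from the time the subject is "administered study medication (Day 1) until Day 28 or early termination".
- Table 1 grid: the AE row is marked at Day 1, Day 7, Day 15, Day 21, Unscheduled and Early Termination. The Day 28 cell is blank. The concomitant-medication row is blank at both Day 28 and Early Termination.

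**Text that runs to Day 28**
- Protocol 12.4.1, the very next sentence: "Subjects with early termination will be followed up until Day 28".
- Protocol 10.1.2 gives a list of procedures that "will be done on Day 7, Day 15, Day 21, Day 28, and early termination by telephone or at onsite visits", and one item is "Review concomitant medications and record any TEAEs".
- Protocol 8.5 asks sites to try to follow discontinued subjects to Day 28 for all outcomes, except after death, hospitalization, withdrawal of consent or loss to follow-up.
- Protocol 6.2.2 has the endpoint "Incidence of AEs and SAEs of any grade from randomization up to Day 28", and its discontinuation endpoint notes follow-up of discontinued subjects to Day 28. SAP 2.3.3 repeats both.
- SAP 4.3.1: "TEAEs will be defined as an AE occurring from Day 1 to end of study which is defined as Day 28".
- Protocol 12.4.3 requires SAE reporting from first dose to Day 28.

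**The concern.** The safety endpoints count events over a fixed 28-day window. SAP 4.3.1 reports numbers, percentages and a relative risk in the Safety Population, which is everyone who took at least one dose. It makes no adjustment for time under observation. A subject whose AE recording stops at withdrawal therefore contributes a shorter look for events but a full unit to the denominator.

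That matters for the comparison only if withdrawal differs between arms in number or timing. Section 8.5 names AEs and SAEs as reasons for leaving the study, so a difference is possible. If more camostat subjects left early, their AE incidence would be the more under-recorded, and the comparison would lean toward no difference.

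Late recording is relevant to this drug by the protocol's own account. Section 5.3 reports that most platelet decreases appeared within 1 month and most hyperkalemia within 2 months of starting, and that some hepatic disorders appeared or were identified after dosing ended.

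**Working it through.** The plan states no figure to reproduce here. The check is a comparison of passages, followed by simple arithmetic on the possible gap.

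**1. Which instruction governs?** Section 10.3 says assessments and their timing follow Table 1. The opening of Section 12 says safety assessments, naming AEs and SAEs, are done at the visits that Table 1 specifies. A site working from Table 1 is therefore following the protocol, and the Day 28 text elsewhere conflicts with that rule without overriding it.

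**2. Does the Day 28 text settle it?** Not fully.
- Section 12.4.1 says both things in consecutive sentences.
- Section 8.5 is a best-efforts clause with exceptions that include hospitalization. Its sentence specific to AEs concerns the event that caused discontinuation, not new events.
- Section 12.4.3 covers serious events only, and Section 12.4.2 says death and inpatient hospitalization are not considered SAEs in this study.
- Section 10.1.2 is clear on both Day 28 and early termination, but it does not match the table.

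**3. Who is affected?** Footnote f speaks of early withdrawal from the study. A subject who stops tablets but stays in the study keeps the remaining scheduled AE checks. A subject who withdraws has one AE check at the Early Termination visit and then, on the footnote's wording, none.

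**4. Gap for one early leaver (illustration).**
- Inputs: last dose on Day 3 (assumed); Early Termination visit 3 to 7 days after last dose (Section 8.5).
- Visit day: 3 + 3 = 6 to 3 + 7 = 10.
- Days left to Day 28: 28 − 6 = 22 to 28 − 10 = 18.
- Share of the window: 22/28 = 79% to 18/28 = 64%.

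**5. Completers.** The last marked AE contact is Day 21, and 28 − 21 = 7 of 28 days (25%) follow it. Footnote f still requires recording to end of study, which Section 7.3 places at Day 28. What is missing is a scheduled prompt, not the obligation to record.

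**6. Scale across the trial (illustration).**
- Planned subject-days: 300 × 28 = 8,400.
- Assumed early leavers: 300 − 279 = 21 (allowance in SAP 4.1.4) or 300 − 275 = 25 (Protocol 13.1). These are allowances for loss or drop-out, not forecasts of withdrawal.
- If all ended AE recording on Day 14: 21 × 14 / 8,400 = 3.5%; 25 × 14 / 8,400 = 4.2%.
- If all ended on Day 3: 21 × 25 / 8,400 = 6.3%; 25 × 25 / 8,400 = 7.4%.
- Under Sections 10.1.2, 12.4.1 (second sentence) and 8.5, the planned gap is zero apart from the Section 8.5 exceptions.

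**7. Footnote tags.** In the text available, the AE row is tagged a and g, and g is the laboratory footnote. Footnote f, which holds the AE rule, is attached to no row.

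**The case against.** The best defence is that the protocol says Day 28 in several places, that Section 10.1.2 is as much a visit instruction as Table 1, and that a competent site would record AEs at the Day 28 call. On that view this is a wording slip, with a literal worst case of a few percent of planned subject-days. Much of this stands, and it limits what may be concluded. A reader might infer four stronger things that the documents do not support:

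- **That harms after stopping are in fact under-counted.** This follows only if sites apply Table 1 literally and disregard the other sections. It is a risk.
- **That the last week goes unobserved in everyone.** Footnote f keeps recording open to end of study for completers, and Section 10.1.2 lists AE recording at the Day 28 call.
- **That anyone who stops study drug is lost to AE recording.** The footnote concerns leaving the study.
- **That the blank concomitant-medication cells hide later COVID-19 treatment.** Section 9.6.1 requires all medication taken during the study to be recorded, and Section 10.1.2 lists the review at Day 28 and early termination.

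There is also a caution about the table. Telephone symbols are missing from its visit row in the text available, so a lost symbol in the Day 28 AE cell cannot be fully ruled out. It is unlikely, because the AE row shows an ordinary mark at Day 21, also a telephone visit, and the body-temperature row shows one at Day 28.

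The defence does not remove the contradiction within Section 12.4.1, or the conflict between Section 10.1.2 and the table that Section 10.3 tells sites to follow.

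**Conclusion.** The plan is internally inconsistent on how long AEs are collected after early withdrawal, and the passages must be reconciled. The exposure is mainly non-serious AEs in subjects who leave the study. For one such subject it is 18 to 22 of 28 days, given an assumed last dose on Day 3. For completers it is one missing prompt.

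Bias in the AE comparison needs two further conditions: sites must work from Table 1 alone, and withdrawal must differ by arm. The documents give no withdrawal times, AE rates or arm-specific withdrawal, so neither the number of missed events nor the direction of any bias can be established. The SAP does not state that every subject is observed to Day 28; that is inferred from its fixed window and full denominators. This is a modest point, worth correcting because the correction is nearly free.

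**What to change.** 1. Reword footnote f and the collection-period sentence of Section 12.4.1 so that AE recording runs to Day 28 for all dosed subjects, including those withdrawn early. The exceptions should match Section 8.5: death, withdrawal of consent and loss to follow-up.
2. Reconcile the hospitalization exception in Section 8.5 with safety endpoints that run to Day 28.
3. In Table 1, add AE and concomitant-medication marks at Day 28 and a concomitant-medication mark at Early Termination, to match Section 10.1.2.
4. Attach footnote f to the AE row and check the present tag.
5. State that early-terminated subjects keep the Day 21 and Day 28 calls.

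The cost is two reworded sentences, three table cells, a footnote tag, and agreement of the exceptions with Section 8.5. The Day 21 and Day 28 calls already exist for subjects on study, so the added burden is one or two short calls for a few early leavers.
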